2.4 Endpoints

Primary Endpoints:

- Within-school tertiary attack rate (TAR) among tertiary TTS participants is defined as transmission from a positive TTS participant to a within-school close contact who enrolled in the TTS study once notified of close-contact status

- Days of school saved is defined as the number of days a participant was allowed to attend in-person work or education after being designated as a close contact instead of being required to undergo school exclusion in the absence of TTS.

Secondary Endpoints:

- Proportion of test-positive participants, including both secondary and tertiary close contacts
- Number of additional school-acquired cases due to TTS.

2.5 Handling of Missing Data

No imputation will be performed; Missing data will be excluded from all denominators.

2.6 Primary Analysis

Primary analysis over the entire study period (11/29/2021–1/28/2022, excluding winter break)

- Objective: Describe demographics for the enrolled and analysis eligible populations
- Objective: Report secondary attack rate and TAR for the enrolled and analysis eligible populations
 - To account for the within-school correlation of outcomes, the 95% confidence interval (CI) for the proportion was estimated using a generalized linear mixed model with districts as a random effect.
 - Re-exposure cases are reported and counted as unique cases.

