2.3 Study Population

- **Enrolled population:** participants with at least one test with valid results.
- **Analysis eligible population:** participants who were tested positive or had a negative follow-up test at day 5 or later, and completed follow-up among those enrolled

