3.3 Study Population

- **Enrolled population:** participants enrolled after household exposures after treating re-exposures within the FU testing period as one long exposures from the first exposure, n=322

Re-exposures after the FU testing period (treat as unique cases)	Re-exposures within the FU testing period (treat as one long exposures) → pick the re-exposed record by A_SL.REEXSEQ in (.2) because two participants got positives after the re-exposure
---	---

Re-exposure records	Confirmed positive	Days to positive, median (min, max)	Note	Re-exposure records	Confirmed positive	Time to positive, median (min, max)	Note
10	5	4 (2, 8)	10 re-exposure records are from 10 participants, which means their initial exposure was not a household close contact.	26	2	8 & 9	26 records are from 13 participants

- **Analysis eligible population:** participants who were tested positive or had a negative follow-up test at day 9 or later, and completed follow-up, n=265

Total records	Exposure period	# enrolled after treating re-exposures (Total records - 13)	# analysis eligible
335	1/8/22 – 2/15/22	322	265

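### Manuscript 2 counts every re-exposure as a unique case with no timing condition, so a participant re-exposed inside an open testing window can enter the attack rates twice; SAP 3.3 merges such records

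*SAP*

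**What the plan says.** SAP 2.6, under the objective of reporting the secondary attack rate (SAR) and tertiary attack rate (TAR), states "Re-exposure cases are reported and counted as unique cases". Nothing in SAP 2.2 to 2.8 limits this to re-exposures after the testing window has closed. Nothing says which record a shared test or positive belongs to. None of the sensitivity analyses in SAP 2.8 varies the choice.

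The rest of Manuscript 2 is worded per person:
- The enrolled population is "participants with at least one test with valid results".
- The analysis eligible population is "participants who were tested positive or had a negative follow-up test at day 5 or later, and completed follow-up among those enrolled".
- A secondary endpoint is "Proportion of test-positive participants, including both secondary and tertiary close contacts".
- Days of school saved counts "the number of days a participant was allowed to attend in-person work or education after being designated as a close contact".
- The interval for the attack rates comes from "a generalized linear mixed model with districts as a random effect", with no participant term.

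SAP 3.3 makes the distinction that SAP 2.6 lacks. Its enrolled population is formed after "treating re-exposures within the FU testing period as one long exposures from the first exposure", and only re-exposures after that period are kept as unique cases.

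**The concern.** A re-exposure inside an open window does not start a fresh, separate observation period. The tests and any positive that follow it also follow the earlier exposure. If both records are kept, the same person and the same result can appear twice in SAR or TAR. The SAP then treats the two records as conditionally independent given district.

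TAR is a primary endpoint of Manuscript 2, and SAR is reported beside it as a main result. The manuscripts come from one SAP and both report SAR and TAR, so a reader comparing them could be comparing different units without being told. The count of extra school-acquired cases attributed to test-to-stay (SAP 2.4) is also exposed, because a positive counted twice there has no denominator to offset it.

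**Working it through.** **1. The SAP's own figure.** SAP 3.3 gives 335 total records, of which 26 within-window records came from 13 participants. Surplus records = 26 − 13 = 13, and 335 − 13 = 322, which is the stated enrolled number. The surplus is 13/335 = 3.9% of all records, or 13/322 = 4.0% of the merged total.

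**2. The two rules side by side.**

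| Timing of re-exposure | Manuscript 2 (SAP 2.6) | Manuscript 3 (SAP 3.3) |
|---|---|---|
| After the testing period | unique | unique |
| Inside the testing period | unique (no exception stated) | merged |

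Only the second row is at issue.

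**3. How far two windows overlap.** Assume tests on days 1, 3, 5 and 7 (SAP Study Design; the protocol allows later changes). For a re-exposure on day k, the calendar days in both windows are k+1 to 7, that is 7 − k days.

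| k | Calendar days in both windows | Tests of the first schedule that also follow the second exposure |
|---|---|---|
| 1 | 6 | 3, 5, 7 |
| 2 | 5 | 3, 5, 7 |
| 3 | 4 | 5, 7 |
| 4 | 3 | 5, 7 |
| 5 | 2 | 7 |
| 6 | 1 | 7 |

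A test on day 5 of the second exposure is day k + 5 of the first. The eligibility rule has no upper limit, so that one negative test can qualify both records. A positive after the re-exposure follows both exposures, so both records can meet the positive criterion.

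**4. Effect on a rate.** Manuscript 2 gives no counts, so this is an assumed range. Let a fraction f of N participants have one overlapping pair, with a true rate p = 10%. The records number N(1 + f).
- (a) Positive kept on one record only: p/(1 + f).
- (b) Pairs positive at the average rate and counted on both records: (p + fp)/(1 + f) = p.
- (c) Extreme, every pair positive and counted on both: (p + f)/(1 + f), for f ≤ p.

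| f | (a) | (b) | (c) |
|---|---|---|---|
| 1% | 9.9% | 10.0% | 10.9% |
| 4% | 9.6% | 10.0% | 13.5% |
| 10% | 9.1% | 10.0% | 18.2% |

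**5. Which case is closer to the data.** The SAP 3.3 table lists 2 confirmed positives for 26 records from 13 people. By person that is 2/13 = 15.4%. By record it is 2/26 = 7.7% if each positive sits on one record, or 4/26 = 15.4% if it sits on both. The listing of 2 suggests one record each, which is case (a), a dilution.

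**6. Effect on the interval.** Compared with one record per person, the nominal standard error shrinks by 1/√(1 + f): 0.995, 0.981 and 0.953 for f = 1%, 4% and 10%, or about 0.5%, 2% and 5%.

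**The case against.** The strongest reply is that SAP 2.6 may be shorthand. SAP 3.3 also calls re-exposures unique, but only those after the testing period, and the authors may have meant the same in Manuscript 2. That is possible, but the text does not say it, and a programmer following SAP 2.6 literally would keep both records.

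Second, exposure-level counting has some support: one of the protocol's primary endpoints (sections 2 and 8.1.1) is a proportion of exposures. The two manuscripts also cover different exposure types and use different eligibility days (5 and 9). This shows that the rules need not be identical. It does not explain why overlapping records should be kept under populations and endpoints worded per participant, and the SAP gives no reason.

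Third, a plain merge dated from the first exposure would create its own fault: someone re-exposed on day 4 would qualify as negative on a day-5 test, one day after the re-exposure. This stands, and the fix has to deal with it.

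A reader might infer three stronger things that the documents do not support:
- That Manuscript 2 did double count. No re-exposure count is given, and an unwritten exception may exist.
- That the attack rates are inflated. The direction is not fixed, and the Manuscript 3 table points more to dilution.
- That days of school saved is overstated. The re-exposure sentence sits under SAR and TAR, the endpoint is defined per participant, and nothing says that days are summed over records. Overstatement would follow only if they were. The overlaps in step 3 are also calendar days, and school days are fewer when a weekend intervenes.

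**Conclusion.** The point holds as a defect in the stated rule. SAP 2.6 has no timing condition, SAP 3.3 has one, and the rule as written lets one person, and one qualifying test or positive, enter SAR or TAR twice under a model with no participant level. Counting re-exposures after the window closes as unique is not a fault, since SAP 3.3 does the same.

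The size in Manuscript 2 cannot be computed. If overlap is about as common as in Manuscript 3, the effect is likely small: roughly 10% reading 9.6% in case (a), with a standard error about 2% too small. This borrows a figure from household exposures and applies it to non-household exposures over a different period, and assumes the day 1, 3, 5 and 7 schedule. A material upward distortion would need much of the overlap to be positive and counted on both records, and nothing in the documents indicates that.

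**What to change.** In SAP 2.6:
- Merge re-exposures that fall inside an open testing window into one episode, and count only later ones as unique, as in SAP 3.3.
- Count each test, each positive and each school day once.
- For analysis eligibility, measure the negative test on day 5 or after from the last exposure in the merged episode.
- Report the number of overlapping records and of participants who contribute them.
- Use a variance clustered at a level that contains the participant, for example school. A separate participant random effect may be poorly estimable when nearly everyone has one record.

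The cost is a few sentences, slightly fewer records, and a re-run of an analysis already submitted: the SAP's history of changes dates the submission and the revision before the plan was documented. The re-run would also show whether any reported result changes.

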2.7 Secondary Analysis

- Objective: The primary analysis will be repeated for during the period when the omicron variant comprised most COVID-19 cases (1/3/2022–1/28/2022)

2.8 Sensitivity Analysis

- Objective: Repeat the main analyses among study participants who had a positive test on or after the day of exposure
- Objective: Repeat the main analyses excluding athletic exposures and exposures acquired outside of school because of the higher risk of transmission previously documented in these settings.
- Objective: Broaden the main analyses for considered positives that include presumed positives, defined as those who developed symptoms but did not receive a subsequent negative test

Manuscript #3 Test-to-Stay in K-12 schools after Household Exposure to SARS-CoV-2

Date	June 14, 2022
Corresponding author	[name]; [name], BS
Lead statistician	[name]
Statistical advisor	[name]
Project leader	[name]
Target journal	TBD

History of changes

Date	Version	Summary of changes
May 6, 2022	1.0	Initial version
June 14, 2022	1.0	Clean up

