3.4 Endpoints

Primary Efficacy Endpoints:

- Days of in-school work and education saved, defined as the number of days a participant could attend in-person work or learning after being notified of a household member who tested positive for SARS-CoV-2.

Safety Endpoints:

- Primary: Tertiary attack rate (TAR) or within-school transmission of SARS-CoV-2, defined as the rate of transmission to within-school close contacts of positive TTS participants
- Secondary: Secondary attack rate (SAR), defined as rate of transmission or test positivity among TTS participants

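### As worded, the first sensitivity analysis in SAP 2.8 and 3.7 selects on the outcome, so its secondary attack rate is 100% by construction (in Manuscript 2, per exposure record)

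*SAP*

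**What the plan says.** The first sensitivity objective is worded the same way for Manuscript 2 (SAP 2.8) and Manuscript 3 (SAP 3.7): "Repeat the main analyses among study participants who had a positive test on or after the day of exposure".

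The analyses to be repeated are attack rates. SAP 2.6 asks the analyst to "Report secondary attack rate and TAR for the enrolled and analysis eligible populations", and 3.6 asks the same for Manuscript 3. The eligible populations in 2.3 and 3.3 admit people who tested positive and also people with a late enough negative test (day 5 or later in Manuscript 2, day 9 or later in Manuscript 3).

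The measures are defined as follows:

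- Manuscript 3 (3.4): "Secondary attack rate (SAR), defined as rate of transmission or test positivity among TTS participants". TAR is measured in the within-school contacts of positive test-to-stay (TTS) participants.
- Manuscript 2 (2.4): a secondary endpoint is "Proportion of test-positive participants, including both secondary and tertiary close contacts". TAR is a primary endpoint, measured in close contacts who themselves enrolled in TTS.
- Manuscript 2 counting unit (2.6): "Re-exposure cases are reported and counted as unique cases".

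Both sensitivity lists also contain an objective that changes what counts as a case; in 2.8 it begins "Broaden the main analyses for considered positives that include presumed positives".

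Separately, SAP 3.6 repeats Manuscript 3's primary analysis for 1/3/2022 to 1/28/2022, labelled as the period when omicron made up most cases. SAP 2.7 uses the same dates. Manuscript 3's exposures run from 1/8/22 to 2/15/22 (3.3). Manuscript 2's data end on 1/28/2022 (2.2).

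**The concern.** A sensitivity analysis of an attack rate has to leave room for the rate to differ from the main result. This one defines its analysis set by the outcome. Once test-negative participants are removed, test positivity among those who remain cannot be anything but complete, so the repeat says nothing about the robustness of SAR.

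What is at stake is SAR in Manuscript 3 (a secondary safety endpoint), SAR and the proportion positive in Manuscript 2, and possibly Manuscript 2's TAR, which is primary. All of this lies within a sensitivity analysis. Whatever robustness question the bullet was meant to answer for these measures is left without a usable specification.

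The omicron window raises a lesser question. In Manuscript 2 it isolates the last part of the data. In Manuscript 3 the same dates discard only the end of the exposure period, and nothing in section 3 explains why the repeat should stop there.

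**Working it through.** **Step 1: can a Manuscript 3 participant contribute more than one household exposure?** SAP 3.3 gives 335 total records. Of the within-period re-exposures, "26 records are from 13 participants", and these are merged: 26 − 13 = 13 records removed, and 335 − 13 = 322, which reproduces the stated enrolled count. For the later re-exposures, "10 re-exposure records are from 10 participants, which means their initial exposure was not a household close contact". No participant is therefore shown with two household exposures among the 322, and participant and exposure are the same counting unit.

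**Step 2: Manuscript 3 SAR under the literal restriction.** Let N be the population size, k the number with any positive test, and b the number whose only positive predates exposure. The documents give neither k nor b.

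- Main analysis: SAR = k/N.
- Literal repeat: only the k − b people with a positive on or after exposure remain, so SAR = (k − b)/(k − b) = 100% for any k > b.
- A case-definition rule: SAR = (k − b)/N, or (k − b)/(N − b), depending on whether the b records stay in the denominator.

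As an illustration with N = 265 (the eligible population in 3.3), b = 0 and k assumed: k = 20 gives 20/265 = 7.5%, and k = 80 gives 80/265 = 30.2%. The literal repeat gives 100% in both cases.

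**Step 3: Manuscript 2.** The unit in 2.6 is the exposure record. With the restriction applied record by record, every record kept is positive, so SAR and the proportion positive are again n/n = 100%. If the filter were applied to people and all their records were then counted, a positive person's other, negative record could remain. The figure could then fall below 100%, but it would still not measure the attack rate.

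**Step 4: TAR.**

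| | Who is counted in the denominator | Effect of the literal restriction |
|---|---|---|
| Manuscript 3 (3.4) | Within-school contacts of positive participants | Not forced: the index set is already positive, and the contacts are not selected on their own result |
| Manuscript 2 (2.4) | Contacts who are themselves enrolled TTS participants | Forced to 100% if the restriction reaches them; not forced if it applies to index participants only |

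**Step 5: omicron window, inclusive calendar days.**

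| | Data or exposure period | Days | In 1/3–1/28 | Cut before | Cut after |
|---|---|---|---|---|---|
| Manuscript 2 | 11/29/2021–1/28/2022 | 61 | 26 | 35 | 0 |
| Manuscript 3 | 1/8–2/15/2022 | 39 | 21 | 0 | 18 |

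For Manuscript 3, 18/39 = 46% of the days, all at the end. The Manuscript 2 count includes winter break, which 2.6 excludes from analysis. The documents do not give the number of participants exposed after 1/28.

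**The case against.** The best reply is that this is loose wording that no analyst would follow. Manuscript 2's change history shows the paper submitted on May 16 and revised on June 14, 2022, before its SAP was documented on June 17. The text may be an imprecise record of a sensible analysis. A natural reading is that only positives dated on or after exposure were to count. That reading is plausible, and I think it is probably right, but it remains an inference: no section states the aim or mentions positives dated before exposure. The SAP also separates the two kinds of change elsewhere. It speaks of broadening the positives when the case definition changes, and of repeating the analyses with exclusions when the population changes. This bullet takes the population form, in both manuscripts.

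It is also fair to say that the restriction is coherent for Manuscript 3's TAR, its primary safety endpoint, because the index participants are positive by definition. That stands, and it limits the damage in Manuscript 3 to SAR.

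A reader might go further and infer that a 100% SAR was computed or reported, or that the submitted manuscript is wrong. The documents do not show how the analysis was run, so that inference is unsupported. SAP 3.7 ends with a note that the team chose to leave something out of the manuscript. It most naturally refers to the imputation exercise just above it, but its scope is unclear, and it does not settle the first bullet.

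On the omicron window, the dates do carry a stated label, and neither 2.7 nor 3.6 promises a contrast with an earlier period. A reader might conclude that the label is false, or that the dates were carried over from 2.7. The documents do not say which variant predominated after 1/28, and the coincidence with Manuscript 2's last data day is only suggestive. What remains is an unexplained end date.

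**Conclusion.** The concern holds as a fault in the written specification. Followed literally, the first sensitivity objective gives a SAR of 100% in Manuscript 3 under either counting unit. In Manuscript 2 it gives 100% for SAR and the proportion positive per exposure record. Manuscript 2's primary TAR is forced as well if the restriction covers the tertiary contacts, which a literal reading does because they are enrolled TTS participants. Manuscript 3's TAR is not forced.

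The result for SAR rests only on the SAP's definitions and the re-exposure counts in 3.3; the values of k in the illustration are assumed and do not affect it. The main SAR and TAR analyses in 2.6 and 3.6 are untouched, so this is no ground for doubting the principal estimates.

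The omicron point is secondary. The window drops the last 18 of 39 calendar days of Manuscript 3's exposures and nothing before them. That supports a request to justify or change the end date, and no more; the all-exposure analysis is unaffected.

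**What to change.** Replace the first bullet in 2.8 and 3.7 with a case-definition rule, for example: *Re-estimate the main measures in both the enrolled and the eligible population, treating a record as a case only if a positive test is dated on or after its exposure date; test-negative records remain in the denominator.*

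The sponsor should then:

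- confirm that this is the intended analysis set;
- state whether a record whose only positive predates exposure leaves both numerator and denominator or stays as a non-case;
- state the counting unit (the exposure record in Manuscript 2, the merged exposure in Manuscript 3);
- for Manuscript 2's TAR, say whether the date rule applies to the index participant, the tertiary participant or both;
- check any sensitivity result already reported against the clarified rule.

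In 3.6, give a reason specific to Manuscript 3 for ending at 1/28, extend the window to 2/15, or drop the repeat. If it stays, make it a separate objective that names SAR and TAR, since it now sits under the demographics and vaccination bullet.

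The cost is a few sentences of SAP text. A re-run on existing data, or a correction, is needed only if the literal wording was followed or the omicron window is changed.

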3.1 Specific Aims

- To describe the utility of a targeted TTS strategy in reducing quarantine duration and limiting missed school days for K-12 students and staff with household exposures

3.2 Data

TTS data collected from K-12 students and staff with household exposures within 4 districts and 1 charter school in North Carolina (NC) employing universal masking.

- Establish population cutoff
 - [name] (Statistical programmer): Here are the number of household exposures with test results on or after days 5, 7, and 9: \geq Day 5 = 282; \geq Day 7 = 251; \geq Day 9 = 214
 - [name] (Project leader): Given that ~65% of population made it into analysis eligible population for day 9, we will use this day as the cutoff, which is consistent with CDC guidance for household close contacts

3.3 Study Population

- **Enrolled population:** participants enrolled after household exposures after treating re-exposures within the FU testing period as one long exposures from the first exposure, n=322

Re-exposures after the FU testing period (treat as unique cases)	Re-exposures within the FU testing period (treat as one long exposures) → pick the re-exposed record by A_SL.REEXSEQ in (.2) because two participants got positives after the re-exposure
---	---

Re-exposure records	Confirmed positive	Days to positive, median (min, max)	Note	Re-exposure records	Confirmed positive	Time to positive, median (min, max)	Note
10	5	4 (2, 8)	10 re-exposure records are from 10 participants, which means their initial exposure was not a household close contact.	26	2	8 & 9	26 records are from 13 participants

- **Analysis eligible population:** participants who were tested positive or had a negative follow-up test at day 9 or later, and completed follow-up, n=265

Total records	Exposure period	# enrolled after treating re-exposures (Total records - 13)	# analysis eligible
335	1/8/22 – 2/15/22	322	265

